5 STUDY OBJECTIVES

5.1 Primary Objective

To evaluate the efficacy of elexacaftor (ELX)/tezacaftor (TEZ)/ivacaftor (IVA) in CF subjects who are heterozygous for *F508del* and a gating or residual function mutation (F/G and F/RF genotypes)

5.2 Secondary Objectives

- To evaluate the safety of ELX/TEZ/IVA
- To evaluate the pharmacodynamics (PD) of ELX /TEZ/IVA

6 STUDY ENDPOINTS

6.1 Efficacy and Pharmacodynamic Endpoints

6.1.1 Primary Endpoint

Absolute change in percent predicted forced expiratory volume in 1 second (ppFEV₁) from baseline through Week 8 for the ELX/TEZ/IVA group

6.1.2 Key Secondary Endpoints

The key secondary efficacy endpoints are as follows:

- Absolute change in sweat chloride (SwCl) from baseline through Week 8 for the ELX/TEZ/IVA group
- Absolute change in ppFEV₁ from baseline through Week 8 for the ELX/TEZ/IVA group compared to the control group
- Absolute change in SwCl from baseline through Week 8 for the ELX/TEZ/IVA group compared to the control group

6.1.3 Other Secondary Endpoints

- Absolute change in CF Questionnaire-Revised (CFQ-R) respiratory domain (RD) score from baseline through Week 8 for the ELX/TEZ/IVA group
- Absolute change in CFQ-R RD score from baseline through Week 8 for the ELX/TEZ/IVA group compared to the control group
- Safety and tolerability assessments based on adverse events (AEs), clinical laboratory values, ECGs, vital signs, and pulse oximetry

6.2 Safety Endpoints

Safety and tolerability will be evaluated via the following endpoints:

[figure not shown]
- Adverse events (AEs)
- Clinical laboratory values
- Standard 12-lead ECGs
- Vital signs
- Pulse oximetry

7 STUDY DESIGN

7.1 Overall Design

This is a Phase 3, randomized, double-blind, active-controlled, parallel-group, multicenter study. A schematic of the study design is shown in Figure 7-1.

Figure 7-1 Schematic of the Study Design

IVA: ivacaftor; ppFEV₁: percent predicted forced expiratory volume in 1 second; SwCl: sweat chloride; TC: triple combination; TEZ: tezacaftor

Note: The Safety Follow-up Visit is not required for subjects who complete the Week 8 Visit and enroll in an open-label study within 28 days after the last dose of study drug.

^a Subjects will be randomized 1:1 to the TC arm or the control arm. Randomization will be stratified based on comparator group (IVA comparator versus TEZ/IVA comparator), ppFEV₁ as determined during the Run-in Period (Day -14 assessment; <70 versus ≥70), and SwCl as determined during the Run-in Period (Day -14 assessment; <30 mmol/L versus ≥30 mmol/L).

In the Run-in Period, subjects will be assigned to the IVA or TEZ/IVA comparator group based on genotype. Subjects assigned to the IVA comparator group will receive IVA 150 mg every 12 hours (q12h) and subjects assigned to the TEZ/IVA comparator group will receive TEZ 100 mg once daily (qd)/IVA 150 mg q12h. The planned dosages for the Treatment Period are shown in Table 7-1.

In the Treatment Period, subjects will be randomized (1:1) to the ELX/TEZ/IVA treatment arm or control arm under a single randomization scheme. Subjects in the control arm who received IVA in the Run-in Period will receive IVA in the Treatment Period; subjects in the control arm who received TEZ/IVA in the Run-in Period will receive TEZ/IVA in the Treatment Period.

Table 7-1 Treatment Period Arms and Planned Dosages

Comparator Group	Treatment Arm	ELX Dosage	TEZ Dosage	IVA Dosage
IVA	ELX/TEZ/IVA	200 mg qd	100 mg qd	150 mg q12h
	Control	0 mg	0 mg	150 mg q12h
TEZ/IVA	ELX/TEZ/IVA	200 mg qd	100 mg qd	150 mg q12h
	Control	0 mg	100 mg qd	150 mg q12h

IVA: ivacaftor; q12h: every 12 hours; qd: once daily; TEZ: tezacaftor

All visits will occur within the windows specified. Please refer to the Table 3-1 and Table 3-2 of the CSP for more details about study visits and assessments.

7.2 Sample Size and Power

The primary efficacy endpoint is the absolute change in ppFEV₁ from baseline through Week 8 for the ELX/TEZ/IVA group. The primary null hypothesis to be tested is that the mean absolute change in ppFEV₁ from baseline through Week 8 is 0 for the ELX/TEZ/IVA treatment group. The null hypothesis will be tested at a 2-sided significance level of 0.05.

For the primary hypothesis, assuming a within-group standard deviation (SD) of 7.0 percentage points and a 10% dropout rate at Week 8, a sample size of 125 subjects in the ELX/TEZ/IVA arm will have >99% power to detect the within group difference of 3.0 percentage points (1 sample t test at a 2-sided significance level of 0.05).

7.3 Randomization

Randomization will be stratified based on comparator group (IVA comparator versus TEZ/IVA comparator), ppFEV₁ as determined during the Run-in Period (Day -14 assessment; <70 versus ≥70), and SwCl as determined during the Run-in Period (Day -14 assessment; <30 mmol/L versus ≥30 mmol/L).

7.4 Blinding and Unblinding

Refer to the CSP section 10.7 for details.

8 ANALYSIS SETS

The following analysis sets are defined: All Subjects Set, Full Analysis Set (FAS), Safety Set for the Run-in Period and Safety Set for the Treatment Period.

8.1 All Subjects Set

The **All Subjects Set** will include all subjects who were randomized or received at least 1 dose of study drug. This analysis set will be used for all individual subject data listings and disposition summary tables, unless otherwise specified.

8.2 Full Analysis Set

The Full Analysis Set (**FAS**) will include all randomized subjects who carry the intended CFTR allele mutation and have received at least 1 dose of study drug in the Treatment Period. The FAS will be used to summarize subject demographics and baseline characteristics, and for all efficacy analyses in which subjects will be analyzed according to their randomized treatment group, unless otherwise specified.

8.3 Safety Set

The **Safety Set for the Run-in Period** will include all subjects who received at least 1 dose of TEZ/IVA or IVA in the Run-in Period. This safety set will be included in individual subject data listings, unless otherwise specified.

The **Safety Set for the Treatment Period** will include all subjects who receive at least 1 dose of study drug in the Treatment Period. This safety set will be used for all safety analyses in which subjects will be analyzed according to the treatment they receive, unless otherwise specified.

9 STATISTICAL ANALYSIS

9.1 General Considerations

The Schedule of Assessments is provided in Section 3 of CSP. The precision standards for reporting safety and efficacy variables are provided in an internal Biometrics document that specifies the programming rules including the precision for derived variables.

Continuous variables will be summarized using the following descriptive summary statistics: the number of subjects (n), mean, standard deviation (SD), median, minimum value (min), and maximum value (max).

Categorical variables will be summarized using counts and percentages. Percentages will be presented to 1 decimal place.

Baseline value, unless otherwise specified, is defined as the most recent non-missing measurement (scheduled or unscheduled) collected before the first dose of study drug in the Treatment Period (i.e., the Day 1 Visit). For ECGs, baseline will be defined as the most recent pretreatment measurement before the first dose of study drug in the Treatment Period (i.e., the Day 1 Visit).

Absolute change from baseline will be calculated as post-baseline value - baseline value.

Relative change from baseline will be calculated as (post-baseline value - baseline value)/baseline value.

The **Treatment-emergent (TE) Period for the Run-in Period** will be from the first dose of study drug in the Run-in Period to (1) the first dose of study drug in the Treatment Period for subjects who complete the Run-in Period and continue to the Treatment Period, or (2) 28 days after the last dose date of study drug in the Run-in Period or to the completion of study participation date, whichever occurs first, for subjects who do not continue to the Treatment Period (e.g., subjects who do not meet the conditions to enter the Treatment Period).

The **TE Period for the Treatment Period** will include the time from the first dose date of study drug in the Treatment Period (TC, placebo + TEZ/IVA, or placebo + IVA) to 28 days after the last dose of the study drug or to the completion of study participation date, whichever occurs first.

Unscheduled visits: Unscheduled visit measurements will be included in analysis as follows:

- 1) In scheduled visit windows per specified visit windowing rules
- 2) In the derivation of baseline
- 3) In the derivation of maximum and minimum values during TE period, and maximum and minimum change from baseline values during TE period for safety analyses
- 4) In individual subject data listings as appropriate

Visit windowing rules: The analysis visit windows for protocol-defined visits are provided in [Appendix A](#).

Incomplete/missing data will not be imputed, unless otherwise specified.

Outliers: No formal statistical analyses will be performed to detect or remedy the presence of statistical outliers, unless otherwise specified.

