3 SCHEDULE OF ASSESSMENTS

Schedules of assessments are in [Table 3-1](#) and [Table 3-2](#).

All visits will be scheduled relative to the Day 1 Visit (first dose of randomized study drug in the Treatment Period). For example, the Week 8 (\pm 5 days) Visit would occur after 8 weeks of study drug administration in the Treatment Period has been completed.

The Cystic Fibrosis Questionnaire-Revised (CFQ-R) must be completed before any other assessment (except signing of the informed consent form [ICF]) at relevant clinic visits. Remaining assessments may be performed in any order when more than 1 assessment is required at a particular time point. All assessments will be performed before study drug dosing (Section 9.6.1), unless noted otherwise.

Table 3-1 Study VX18-445-104: Screening

Event/Assessment	Screening Period Day -56 Through Day -29	Comments
ICF and assent (when applicable)	X	
Inclusion and exclusion criteria review	X	Sections 8.1 and 8.2
Demographics	X	Section 11.1
Medical history	X	
CFTR genotype	X	Performed for all subjects (Section 11.6.2). In subjects with an R117H mutation, linkage to poly-T tract polymorphisms will also be determined from a second specimen. A subject's screening CFTR genotype must confirm eligibility before the subject enters the Run-in Period (Section 8.1).
FSH	X	Performed for any suspected postmenopausal female with at least 12 months of continuous spontaneous amenorrhea (Section 11.6.2)
Serum pregnancy test (all females)	X	Section 11.6.2
Hematology	X	
Coagulation	X	
Serum chemistry	X	
Urinalysis	X	
Weight and height	X	Measured with shoes off (Section 11.1)
OE	X	Conducted only for subjects who are <18 years of age on the date of informed consent (Section 11.6.6)
Complete physical examination	X	Section 11.6.3
Vital signs	X	Performed after subject has been at rest for at least 5 minutes (Sections 11.6.3, 11.6.4, and 11.6.5)
Pulse oximetry	X	
Standard 12-lead ECG	X	
Spirometry	X	May be performed pre- or post-bronchodilator (Section 11.5.1)
Medications review	X	Section 9.5
Sweat chloride	X	Section 11.3
AEs and SAEs	Continuous from signing of the ICF through completion of study participation	Sections 9.1.7, 13.1.1.3, and 13.1.2.2

AE: adverse events; FSH: follicle-stimulating hormone; ICF: informed consent form; OE: ophthalmologic examination; SAE: serious adverse event

Table 3-2 VX18-445-104: Run-in Period, Treatment Period, and Safety Follow-up Visit

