12.3 Statistical Analysis

12.3.1 General Considerations

Continuous variables will be summarized using the following descriptive summary statistics: the number of subjects (n), mean, SD, median, minimum value (min), and maximum value (max). The precision of the measurement for each continuous variable will be specified in the SAP. Unless otherwise specified, min and max values will be reported with the same precision as the units of the raw data. The mean, median, and SD will be reported to 1 additional decimal place. Any values that require a transformation to standard units (metric or SI) will be converted with the appropriate precision.

Categorical variables will be summarized using counts and percentages. Percentages will be presented to 1 decimal place.

The **baseline value**, unless otherwise specified, will be defined as the most recent non-missing measurement (scheduled or unscheduled) collected before the first dose of study drug in the Treatment Period (i.e., the Day 1 Visit). For ECGs, baseline will be defined as the most recent pretreatment measurement (or the average of triplicate measurements, if the most recent pretreatment measurement is obtained in triplicate) before the first dose of study drug in the Treatment Period (i.e., the Day 1 Visit).

Absolute change from baseline will be calculated as post-baseline value – baseline value.

The **Treatment-emergent (TE) Period for the Run-in Period** will be from the first dose date of study drug in the Run-in Period to (1) the first dose date of study drug in the Treatment Period for subjects who complete the Run-in Period and continue to the Treatment Period, or (2) 28 days after the last dose date of study drug in the Run-in Period or to the completion of study participation date, whichever occurs first, for subjects who do not continue to the Treatment Period (e.g., subjects who do not meet the conditions to enter the Treatment Period).

The **TE Period for the Treatment Period** will include the time from the first dose of study drug in the Treatment Period (TC, placebo + TEZ/IVA, or placebo + IVA) to 28 days after the last dose of study drug or to the completion of study participation date (as defined in Section 9.1.7), whichever occurs first.

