9.4.2 Clinical Laboratory

For the treatment-emergent laboratory assessments, the observed values and change from baseline values of the continuous hematology, coagulation and chemistry results will be summarized in SI units at each visit by treatment group.

The number and percentage of subjects meeting at least 1 threshold analysis criterion event, during the TE period for Treatment Period, will be summarized by treatment group. The threshold analysis criterion shift from baseline will also be summarized for selected laboratory parameters. The threshold analysis criteria are provided in [Appendix F](#).

For selected LFT laboratory test (alanine transaminase [ALT], aspartate transaminase [AST], alkaline phosphatase [ALP], and total bilirubin), a scatter plot of the maximum treatment-emergent value versus the baseline value corresponding to \times ULN (upper limit of normal) will be presented. Further, a scatter plot of the maximum treatment-emergent value of ALT and AST,

separately, versus the maximum treatment-emergent value of total bilirubin corresponding to \times ULN will also be presented by treatment group.

Results of positive urine/serum pregnancy test will be listed in individual subject data listings only. For positive serum pregnancy listing, subjects with serum HCG which are abnormally high will be selected.

In addition, a listing containing individual subject hematology, chemistry, coagulation and urinalysis values will be provided. This listing will include data from both scheduled and unscheduled visits.

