12 LIST OF APPENDICES

Appendix A: Analysis Visit Windows for Safety and Efficacy Assessment

Table 12-1 Analysis Visit Windows for Safety and Efficacy Assessments

Assessment	Visit ¹	Target Study Day	Analysis Visit Window ^{2,3,4} (in study days)
Safety Assessment			
Serum Chemistry Hematology Standard 12-lead ECG	Day 1 (Baseline)	1	≤1 Pre-dose
	Day 15	15	[1, 22]
	Week 4	29	(22, 43]
	Week 8	57	(43, 71]
	Safety Follow-up	Not applicable	Use nominal visit
Coagulation	Day 1 (Baseline)	1	≤1 Pre-dose
	Week 8	57	[1, 71]
	Safety Follow-up	Not applicable	Use nominal visit
Vital Signs (excluding BMI, Weight, Height)	Day 1 (Baseline)	1	≤1
	Day 15	15	[1,22]
	Week 4	29	(22, 43]
	Week 8	57	(43, 71]
	Safety Follow-up	Not applicable	Use nominal visit
Efficacy Assessment and Pharmacodynamic Assessment			
Spirometry ⁵	Day 1 (Baseline)	1	≤1 Pre-dose
	Day 15	15	(1,22]
	Week 4	29	(22, 43]
	Week 8	57	(43, 71]
	Safety Follow-up	Not applicable	>71
Sweat Chloride	Day 1 (Baseline)	1	≤1 Pre-dose
	Day 15	15	(1,22]
	Week 4	29	(22, 43]
	Week 8	57	(43, 71]
CFQ-R Weight, Height and BMI ⁵	Day 1 (Baseline)	1	≤1
	Day 15	15	(1,22]
	Week 4	29	(22, 43]
	Week 8	57	(43, 71]
	Safety Follow-up	Not applicable	>71
Notes:			
¹ Visit name for analysis purpose is used to report data in tables and figures.			
² The analysis visit windows will be applied using the following rules for both scheduled and unscheduled visits:			
a. If no numerical measurement is available within a visit window, the measurement will be considered missing for the visit.			
b. If there is more than 1 numerical measurement available within a visit window, use the following rules:			
i. The measurement closest to the target day will be used; or			
ii. If there are multiple measurements with the same distance from the target day, the latest measurement will be used. If the latest measurement cannot be determined, then unscheduled visit will be selected.			
³ For measurement collected on the date of first dose of study drug in Treatment Period, if it cannot be determined whether the measurement is before or after the first dose:			
a. Scheduled measurement will be treated as pre-dose observation.			

Table 12-1 Analysis Visit Windows for Safety and Efficacy Assessments

Assessment	Visit ¹	Target Study Day	Analysis Visit Window ^{2,3, 4} (in study days)
b. Unscheduled measurement will be treated as post-dose observation.			

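### SAP 9.1 starts the Treatment Period treatment-emergent window at the first-dose date, so a literal reading takes in pre-dose Day 1 safety values

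*SAP*

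**What the plan says.** **TE boundaries.** Protocol 12.3.1: the TE Period for the Treatment Period "will include the time from the first dose of study drug in the Treatment Period". SAP 9.1: it "will include the time from the first dose date of study drug in the Treatment Period". For subjects who go on to randomised drug, the SAP ends the Run-in TE Period at "the first dose of study drug in the Treatment Period for subjects who complete the Run-in Period and continue to the Treatment Period"; the protocol ends it at "the first dose date of study drug in the Treatment Period for subjects who complete the Run-in Period and continue to the Treatment Period". SAP 3.1 declares no modification to the protocol.

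**Timing of Day 1 measurements.** Protocol Section 3: "All assessments will be performed before study drug dosing (Section 9.6.1), unless noted otherwise". Table 3-2 schedules chemistry, hematology, coagulation, ECG, vital signs and pulse oximetry on Day 1.

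**What uses the TE Period.** SAP 9.1 also uses unscheduled measurements "In the derivation of maximum and minimum values during TE period". SAP 9.4.2 to 9.4.4 count subjects who meet at least one threshold criterion in the TE Period. SAP 9.4.5 takes the lowest oxygen saturation in it. For liver tests SAP 9.4.2 plans "a scatter plot of the maximum treatment-emergent value versus the baseline value".

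**What sorts Day 1 values.** SAP 9.1 takes baseline as the last value before the first Treatment Period dose. Table 12-1 limits the baseline window to pre-dose for chemistry, hematology, ECG and coagulation, but not for vital signs. Footnote 3 covers Day 1 values of unknown timing: scheduled ones are treated as pre-dose, unscheduled ones as post-dose.

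**The concern.** A summary labelled treatment-emergent should describe what happened after randomised drug began. If the window opens at the start of the calendar day, the Day 1 safety panel, taken on run-in drug, falls inside it. One record can then be both the baseline and a treatment-emergent value.

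An abnormality present before the first randomised dose, and gone afterwards, could then be counted as an event on randomised treatment. Separately, the vital-sign windows would let a Day 1 reading stand in for a missing Day 15 value, with a change of 0. An adverse event that starts on Day 1 could appear both in the Run-in tables planned in SAP 9.4.1 and in the Treatment Period tables.

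**Working it through.** The plan gives no figure for this point, so the check sets the rules side by side.

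**1. Boundaries**

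| | Run-in TE Period ends at | Treatment TE Period starts at |
|---|---|---|
| Protocol 12.3.1 | first dose date | first dose |
| SAP 9.1 | first dose | first dose date |

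Under the SAP's pair, the part of Day 1 before the dose belongs to both periods. The adverse-event definitions differ in the same way: Protocol 12.3.4.1 uses the first dose, SAP 9.4.1 the first dose date.

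**2. Does another rule take pre-dose values out?** The baseline definition, the pre-dose limit in Table 12-1 and footnote 3 decide which record is baseline and how a record is windowed. None says that a baseline record is outside the TE Period. Threshold counts, maxima, minima and lowest saturation are defined by that period, not by visit windows. For ECGs, Appendix A uses every reported value on a TE day for threshold purposes. Table 12-1 names no pulse-oximetry row.

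**3. Effect on each display.** Let B be a baseline dated Day 1 and x1 to xk the post-dose values.

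- Scatter plot: max(B, x1, …, xk) ≥ B, so that subject cannot fall below the diagonal.
- Lowest saturation: min(B, x1, …, xk) ≤ B, so low at baseline and normal afterwards is shown as low to low.
- Change-from-baseline criteria: B − B = 0, so a Day 1 value that is the baseline cannot meet one. This includes the combined criteria in Tables 12-4 and 12-5.
- Absolute thresholds: in an arm, let n be the share newly abnormal after dosing, s the share abnormal before and after, and r the share abnormal only before. Counting from the dose gives n + s. Counting from the date gives n + s + r. The excess is r, the subjects whose abnormality resolved. If r is equal in both arms, the absolute difference is unchanged. If one arm resolves more, the date-based count hides that.

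The documents give no value for r. With 250/2 = 125 subjects in an arm, each such subject adds 1/125 = 0.8 percentage points.

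**4. Visit windows in Table 12-1**

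| Row | Baseline | First later window | Pre-dose Day 1 value fits both | Post-dose Day 1 value fits both |
|---|---|---|---|---|
| Chemistry, hematology, ECG | ≤1 Pre-dose | [1, 22] | yes, by day number | no |
| Coagulation | ≤1 Pre-dose | [1, 71] | yes, by day number | no |
| Vital signs | ≤1 | [1, 22] | yes | yes |
| Spirometry, sweat chloride | ≤1 Pre-dose | (1, 22] | no | no |
| CFQ-R, weight, height, BMI | ≤1 | (1, 22] | no | no |

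Only the vital-sign row joins an unqualified baseline to a closed bracket at 1. In the laboratory and ECG rows the bracket can be read as admitting post-dose Day 1 values, but the table does not say so.

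The value nearest the target day is used. Day 1 is |1 − 15| = 14 days from the Day 15 target. Day 2 is 13 days away and Day 22 is 7, so a Day 1 reading fills Day 15 only if nothing exists on Days 2 to 22.

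**The case against.** The strongest reply is that the intent is plain. Baseline is the last value before the first dose, change is post-baseline minus baseline, and the scatter plot sets the TE maximum against baseline as a separate quantity. Footnote 3 is attached to the window column, so it reaches vital signs too. The protocol itself uses dose and dose date unevenly, which suggests loose drafting rather than a deliberate change. Safety is descriptive with no testing (SAP 9.4), and shift tables for selected laboratory parameters will show that an abnormality was already present.

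Most of this stands. It shows what was meant and keeps the consequences small. It does not supply the missing exclusion: footnote 3 applies only when timing cannot be determined, and labelling a record pre-dose does not remove it from a period that opens on that date.

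Four stronger readings are tempting, and the documents do not support them.

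- A reader might infer that the SAP has settled on counting baseline values as treatment-emergent. It has not said so; that outcome needs the boundary to be applied by date alone.
- A reader might infer that arm differences in safety are generally hidden. An equal rise in both arms leaves the absolute difference as it was. What can be lost is resolution.
- A reader might infer that every scatter-plot point is forced onto or above the diagonal. That holds only under the literal reading and for baselines dated Day 1.
- A reader might infer that adverse events need a date-and-time boundary. Protocol 13.1.1.3 lists the date of first occurrence and no clock time, so such a rule could not be applied to the data listed. A date convention is reasonable there.

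**Conclusion.** The point holds as a wording defect with a limited reach. As written, the SAP's Treatment TE Period includes pre-dose Day 1, departs from the protocol without declaring it, and overlaps the SAP's own Run-in TE Period. The vital-sign row of Table 12-1 has a separate overlap that matters only when no reading exists on Days 2 to 22.

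The displays exposed are absolute-threshold counts, TE maxima and minima, the liver-test scatter plots and the lowest-saturation shift. The possible error is that resolution of earlier abnormalities is masked. The size cannot be stated, because the documents give no rate of pre-dose abnormality that later resolves. No hypothesis test, error rate or efficacy result depends on it.

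The conclusion assumes that the TE boundary is programmed as the SAP words it. If pre-dose records are already excluded in programming, the outputs are right and only the text needs correcting.

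**What to change.** - **SAP 9.1, measured safety values** (laboratory, ECG, vital signs, oximetry): start the Treatment TE Period at the first Treatment Period dose, as in the protocol. State that records classed as pre-dose are excluded from maxima, minima, threshold counts and lowest saturation, with footnote 3 applied where timing is unknown.
- **Table 12-1:** change the vital-sign baseline window to ≤1 Pre-dose, and state that every window opening with a closed bracket at 1, including the laboratory, ECG and coagulation rows, takes post-dose values only.
- **Adverse events:** keep the date-based start in SAP 9.4.1, but end the Run-in TE Period before the first Treatment Period dose date, so that a Day 1 onset counts in one period only. SAP Table 12-2 already splits medications this way, with a strict inequality on the Run-in side.

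The cost is a few words in the SAP and a pre-dose or post-dose flag on Day 1 records; no new data are needed. SAP Section 4 allows an amendment before database lock. After lock, the clarification belongs in the clinical study report.
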